5.3.1.2. Between group

A formal non-inferiority analysis with a non-inferiority margin of 5 will be performed. Non-inferiority assessment will be carried out based on the fact that the distribution of two Poisson variates conditional on their sum is binomial [Lehmann, 1959]. Let n_1 and n_0 be the number of HZ recurrence cases, T_1 and T_0 (years) be total follow up, and r_1 and r_0 be the incidence rate in HZ/su group and placebo group respectively. It is assumed that $n_i \sim \text{Poisson}(\lambda_i)$ ($i=0,1$) and $\lambda_i = T_i \times r_i$, and condition on $n = n_0 + n_1$, $n_1 \sim \text{Binomial}(n, p)$, where $p = \lambda_1 / (\lambda_1 + \lambda_0)$. A 95% exact CI for p can be derived by using Clopper-Pearson approach, through which a 95% exact CI for $\pi = r_1 / r_0$ (that is, the ratio of incidence rate of HZ recurrence (HZ/su versus placebo)) can be derived. Non-inferiority is met if the upper limit of the 95% CI for π is below 5.

In addition to performing a formal non-inferiority analysis, to further quantify the likelihood of the risk increase of HZ following *Shingrix* vaccination, a probability curve that the ratio of incidence of HZ recurrence (HZ/su versus placebo) is higher than x -fold (x varying from 1 to 5) will be estimated by Bayesian methodology. It will be assumed that the number of HZ cases in the HZ/su and in placebo groups follows Poisson distribution with rate (incidence rate) of λ_{HZ} and λ_P respectively. We further assume that λ_{HZ} and λ_P are random variables both with non-informative Gamma prior distribution: Gamma (0.001, 0.001). Based on the posterior distribution of λ_{HZ} and λ_P , the probability curve of the ratio of incidence of HZ recurrence (HZ/su versus placebo), that is, $\text{Pr}(\lambda_{HZ}/\lambda_P > x | \text{data, prior})$, can be calculated for each given value of x .

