5.3.2. Additional considerations

For analysis for non-inferiority, only the first confirmed HZ episode will be considered. The non-inferiority will be assessed by following model and fitted via the PROC GENMOD procedure according to the following code:

```
PROC GENMOD data=XXX;
  CLASS group_nb(ref="Placebo") / param=ref;
  MODEL nb_cases = group_nb / dist=poisson offset=log_T link=log type3;
```

```

EXACT group_nb / estimate=odds;
ODS OUTPUT ExpExactParmEst=IRR;
RUN;

```

where,

nb_case = number of cases

Group_nb = Group information of the subject (treatment received by subject)

Log_T = Log of the follow-up time

Note: variables names may vary as per ADAM variables however their derivations remain the same.

The estimated rate ratio and its 95% CI will be provided in the output dataset IRR.

In extreme situations, when there are no confirmed HZ cases in the HZ/su group and > 0 confirmed HZ cases in the Placebo group, the EXACT computational algorithm used in SAS will run into difficulty and cannot provide accurate results. Therefore, the rate ratio (HZ/su versus placebo) will be set to 0. When there are no confirmed HZ cases in the Placebo group and > 0 confirmed HZ cases in the HZ/su group, the rate ratio is not estimable, instead the incidence rate and 95% CI in each treatment group will be reported.

- For Bayesian analysis, the number of HZ cases in the HZ/su and in placebo groups follows Poisson distribution with rate (incidence rate) of λ_{HZ} and λ_P , respectively. We further assume that λ_{HZ} and λ_P are random variables both with non-informative Gamma prior distribution: Gamma (0.001, 0.001). The posterior distribution of λ_{HZ} and λ_P will be Gamma distribution with parameter

$\lambda_{HZ} \sim \text{Gamma}(0.001 + case_{HZ}, 0.001 + T_{HZ})$ and

$\lambda_P \sim \text{Gamma}(0.001 + case_P, 0.001 + T_P)$

where,

$case_{HZ}$ = number of cases in HZ/su group

$case_P$ = number of cases in placebo group

T_{HZ} = total follow-up time in years in HZ/su group

T_P = total follow-up time in years in placebo group

To estimate the probability of incidence rate ratio, simulation program will be run to generate sample from Gamma distribution using the function above.

The probability of incidence rate ratio greater than a specified value (e.g., 1, 2, 3, 4, 5) will be plotted against incidence rate ratio in graph.

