6. ANALYSIS INTERPRETATION

The primary objective of non-inferiority of the incidence of HZ recurrence in the HZ/su and placebo groups is considered met if the upper limit of the 95% CI of the ratio of the incidence of HZ recurrence (HZ/su versus placebo) is below 5.

For all secondary objectives, analyses will be descriptive with the aim to characterize the differences in reactogenicity, safety and immunogenicity between groups.

The ratio of incidence of HZ recurrence (HZ/su versus Placebo) calculated using Bayesian methodology will be a descriptive analysis to provide additional information about incidence rate ratio between Hz/su and Placebo based on simulated data with assumption provided (sections [5.3.1.2](#) and [5.3.2](#)) of the SAP.

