- The follow-up time at risk is computed using the following formula:
 - **stop – start +1.**

The **time at risk** will be expressed in Person-Year and derived from the follow up time (follow up time in days/365.25).

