9.2. Statistical Method

9.2.1. HZ incidence

The number of HZ incidence is assumed to follow the Poisson distribution. The estimated incidence rate with 95% CI for both groups will be computed using following formula:

Incidence rate (per 1000) = Number of events*1000/Total follow-up period (in days)
=n*1000/T

$$\text{Exact LL of incidence rate} = \frac{X_{2n,\alpha/2}^2}{2T}$$

$$\text{Exact UL of incidence rate} = \frac{X_{2(n+1),(1-\frac{\alpha}{2})}^2}{2T}$$

Where $X_{v,\alpha}^2$ is the chi-square distribution quantile for upper tail probability on v degrees of freedom, n is the number of events and T is the total follow-up time [Ulm, 1990]. Rule to derive the total follow-up period (in days) is provided in section 9.1.3 of the SAP.

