9.2.2. Safety

The ~~CI~~ and other HZ related complication is assumed to follow Poisson distribution and will be estimated for both the groups with 95% CI using the formula provided in the section 9.2.1 of the SAP.

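### SAP 9.2.1, coded as written, gives wrong per-group 95% confidence limits for HZ incidence: the tail wording is reversed and the limits lack the factor of 1000

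*SAP*

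**What the plan says.** SAP 9.2.1 introduces one estimate with its interval: "The estimated incidence rate with 95% CI for both groups will be computed using following formula". Three expressions follow, with n the number of events and T the total follow-up:

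- Rate: "Incidence rate (per 1000) = Number of events*1000/Total follow-up period (in days"), that is, n × 1000 / T.
- Exact lower limit: chi-square with subscripts 2n and alpha/2, divided by 2T.
- Exact upper limit: chi-square with subscripts 2(n+1) and 1-alpha/2, divided by 2T.

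The section then says that the chi-square symbol "is the chi-square distribution quantile for upper tail probability on v degrees of freedom".

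Other sections bear on the formula:

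- SAP 9.1.3 puts time at risk in a different unit: it "will be expressed in Person-Year and derived from the follow up time (follow up time in days/365.25").
- SAP 9.2.2 estimates HZ-related complications with 95% CIs "using the formula provided in the section 9.2.1 of the SAP".
- SAP 5.3.2 covers the case of no confirmed cases on placebo and at least one on HZ/su: "the rate ratio is not estimable, instead the incidence rate and 95% CI in each treatment group will be reported".
- SAP 5.3.1.2 builds the primary interval differently: "A 95% exact CI for p can be derived by using Clopper-Pearson approach".
- SAP 5.3.1.1 tabulates the per-group incidence rate but does not mention an interval.
- SAP 6 sets the status of the rest: "For all secondary objectives, analyses will be descriptive".

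**The concern.** There are two separate defects.

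**Tails.** If the subscript is an upper-tail probability, alpha/2 = 0.025 selects the 97.5th percentile and 1-alpha/2 = 0.975 selects the 2.5th. The lower limit then takes the high percentile and the upper limit the low one. The formula and the definition of its symbol contradict each other.

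**Scale.** The rate is per 1000 and the limits are per 1. They are presented as one estimate with its interval, so the estimate falls outside its own limits whichever tail convention is used.

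The per-group HZ incidence intervals and the intervals for HZ complications depend on this formula. It is also the SAP's only stated per-group interval formula, so it would supply the intervals reported in place of the ratio if placebo had no cases. The non-inferiority decision does not depend on it.

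**Working it through.** **Inputs.** Protocol 11.4 gives 0.55% per year on placebo, 0.275% on HZ/su, two years of follow-up and 606 evaluable subjects per group. These figures reproduce: 10 cases / (2 × (0.0055 + 0.00275)) = 606.06, and 606 / 0.85 = 713 enrolled. The plan gives no worked number for the 9.2.1 formula, so I illustrate it at

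- T = 606 × 2 = 1212 person-years (× 365.25 = 442,683 days);
- expected cases: 1212 × 0.0055 = 6.67 on placebo and 1212 × 0.00275 = 3.33 on HZ/su. I use 7 and 3.

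**Tails.** Below, q(p; v) is the lower-tail chi-square quantile, and limits are on the count scale (before dividing by T).

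- Standard exact limits: q(0.025; 2n)/2 and q(0.975; 2n+2)/2.
- As worded: lower limit q(0.975; 2n)/2, upper limit q(0.025; 2n+2)/2.

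| n | Correct lower, upper | As worded: lower, upper |
|---|---|---|
| 0 | 0, 3.689 | undefined, 0.0253 |
| 3 | 0.619, 8.767 | 7.225, 1.090 |
| 7 | 2.814, 14.423 | 13.059, 3.454 |

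Multiplying by 1000/1212 gives rates per 1000 person-years:

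| n | Rate | Correct lower, upper | Tail error alone: lower, upper |
|---|---|---|---|
| 0 | 0 | 0, 3.04 | undefined, 0.021 |
| 3 | 2.48 | 0.51, 7.23 | 5.96, 0.90 |
| 7 | 5.78 | 2.32, 11.90 | 10.78, 2.85 |

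The lower limit exceeds the upper for every n checked, from 1 to 1999. At n = 0 the upper limit is too small by a factor of 145.7, and the lower limit calls for a quantile on 0 degrees of freedom. The correct limits were confirmed against Poisson tails: at n = 3 and n = 7 each tail probability is 0.025.

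**Scale.** With the tails corrected but without the factor of 1000, 7 cases give a rate of 7 × 1000 / 1212 = 5.78 beside limits 2.814/1212 = 0.0023 and 14.423/1212 = 0.0119. With T in days, as 9.2.1 writes it, 3 cases give 0.00678 per 1000 person-days beside 0.0000014 to 0.0000198. The upper limit lies below the estimate for every n from 1 to 1999.

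**Would swapping the two printed columns repair the tails?** No, because the degrees of freedom then sit on the wrong limits. The relabelled interval for 7 cases is 3.454 to 13.059 on the count scale, with width 9.606/11.608 = 83% of the correct one. For 3 cases it is 1.090 to 7.225, with width 6.135/8.149 = 75%. For expected counts from 3 to 7 (0.01 grid, lower limit 0 at n = 0), its coverage runs from 84.8% to 94.8%, against 95.9% to 99.1% for the correct limits. If the n = 0 upper limit is also put right, the relabelled range is 84.8% to 97.5%.

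**The fallback in 5.3.2.** With 6.666 placebo cases expected, P(no placebo cases) = exp(-6.666) = 0.13%. Requiring at least one HZ/su case as well gives 0.0012735 × (1 - exp(-3.333)) = 0.12%.

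**The case against.** The strongest reply is that the formula itself is sound. Read as lower-tail quantiles, the subscripts and degrees of freedom are exactly the standard exact Poisson limits, and only the wording of the definition is off. A programmer who knows the method, or uses a quantile function that takes cumulative probabilities, would get the tails right. One who followed the wording would see inverted limits in any arm with at least one case. This stands as a reason for a low rating. It does not remove the contradiction, and it does nothing for the scaling.

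On scaling, only the rate is labelled per 1000, so the limits could be meant for the unscaled rate. The sentence that introduces the formulas presents one estimate with its CI, which tells against that reading. The literal output would also be conspicuous.

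Nothing in the SAP suggests that anyone would merely swap the printed columns. The width and coverage figures therefore describe a hypothetical bad repair. They show why the text should be corrected at source and do not measure an error already in the plan.

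Finally, the subscripts were read by machine from a PDF and should be checked in the original. A reading fault is unlikely to explain both defects: the definition is plain prose, and the factor of 1000 is absent from both limits.

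**Conclusion.** The concern holds, as a minor one. As written, SAP 9.2.1 yields inverted limits for any arm with cases, an upper limit about 146 times too small for an arm with none, and limits a factor of 1000 away from the estimate they accompany. The inversion and the factor of 1000 do not depend on the follow-up time; the illustrated rates do, and they assume 1212 person-years per group. The difference in time unit between 9.1.3 and 9.2.1 only rescales the rate and does not distort the interval.

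The consequences are limited to descriptive per-group intervals for HZ incidence and HZ complications, plus the rarely needed fallback in 5.3.2. The primary non-inferiority interval (5.3.1.2, fitted as in 5.3.2) is unaffected.

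**What to change.** In SAP 9.2.1:

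1. Define the chi-square symbol as the lower-tail (cumulative) quantile. Alternatively, keep the upper-tail definition and swap the subscripts, so that the lower limit uses 1-alpha/2 and the upper limit alpha/2. Either change reproduces the correct limits (7 cases: 2.32 to 11.90; 3 cases: 0.51 to 7.23). Do not simply swap the output columns.
2. Multiply both limits by 1000.
3. State that the lower limit is 0 when n = 0.
4. For clarity, give T in person-years, in line with 9.1.3, and label the estimate and limits per 1000 person-years.

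Section 9.2.2 takes up the correction through its cross-reference. The cost is SAP wording only, with no change to the design, the data or the primary analysis.

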9.2.2. Safety

The ~~CI~~ and other HZ related complication is assumed to follow Poisson distribution and will be estimated for both the groups with 95% CI using the formula provided in the section 9.2.1 of the SAP.

10. ANNEXES

10.1. Business rules for standard data derivations and statistical methods

This section contains GSK Vaccines' standard rules for data display and derivation for clinical and epidemiological studies. These rules will be applied along with those detailed in section 9 (additional study-specific rules).

10.1.1. Attributing events to vaccine doses

The dose relative to an event is the most recent study dose given to a subject prior to the start of a given event. For example, if the start date of an AE is between Dose 1 and Dose 2, the relative dose will be Dose 1.

If an event starts on the same day as a study dose, the relative dose will be derived from the additional information provided in the CRF using the contents of the flag indicating if the event occurred before or after vaccination. If 'after vaccination' is selected, the relative dose for the event will be the one administered on the start day of the event. If 'before vaccination' is selected, the relative dose for the event will be the dose prior to this one.

10.1.2. Handling of missing data

10.1.2.1. Dates

When partially completed dates (i.e. with missing day or month) are used in calculations, the following standard rules will be applied:

- A missing day will be replaced by 15
- A missing day and month will be replaced by June 30th.

The following exceptions apply:

- AE start dates with missing day:
 - If the event starts in the same month as at least one of the study doses, the contents of AE.AESTRTPT (the flag indicating if the event occurred before or after vaccination) will be used to complete the date. If 'after vaccination' is selected, the imputed start date will match the first (or only) study dose given during that month. If 'before vaccination' is selected, the imputed date will be one day before the first (or only) study dose given during that month.
- AE start dates with missing day and month:
 - If the event starts in the same year as at least one of the study doses, the contents of AE.AESTRTPT (the flag indicating if the event occurred before or after vaccination) will be used to complete the date. If 'after vaccination' is selected, the imputed start date will match the first (or only) study dose given during that

year. If ‘before vaccination’ is selected, the imputed date will be one day before the first (or only) study dose given during that year.

All other cases of incomplete AE or concomitant medication/vaccination start date will follow the standard rules above.

10.1.2.2. Laboratory data

Missing laboratory results (including immunological data) will not be replaced.

10.1.2.3. Daily recording of solicited adverse events

10.1.2.3.1. Studies with paper diaries

For studies using paper diaries which have questions in the CRF indicating the presence or absence of solicited AEs, the following rules are applicable.

Denominators for the summary of local (or general) solicited AEs will be calculated using the number of subjects who respond “Yes” or “No” to the question concerning the occurrence of local (or general) AEs.

When a specific solicited AE is marked as having not occurred following a specific vaccination (i.e. SDTM CE.CEOCCUR=N for the specified post-vaccination period for the AE in question), all daily measurements will be imputed as Grade 0.

When a specific solicited AE is marked as having occurred following a specific vaccination (i.e. SDTM CE.CEOCCUR=Y for the specified post-vaccination period for the AE in question), any missing daily recordings will be given imputed values to allow them to contribute to the ‘Any’ rows but not to specific grade rows of the solicited AE summary tables.

When the occurrence of a specific solicited AE is not present (i.e. SDTM CE.CEOCCUR is neither Y nor N for the specified post-vaccination period for the symptom in question) but the group of solicited AE (local or general) is marked as having occurred (i.e. SDTM CE.CEOCCUR=Y), all missing daily recordings will be given imputed values to allow them to contribute to the ‘Any’ rows but not to specific grade rows of the solicited AE summary tables.

The following table shows how subjects contribute to each category for a specific solicited AE over the Day X to Day Y post-vaccination period:

Solicited adverse event category	Subjects included in the calculation of the numerator
Any	All subjects with at least one occurrence of the adverse event at grade 1, grade 2, or grade 3 between Day X and Day Y or with the adverse event marked as present and at least one missing daily recording between Day X and Day Y
At least grade 1	All subjects with at least one occurrence of the adverse event at grade 1, grade 2, or grade 3 between Day X and Day Y
At least grade 2	All subjects with at least one occurrence of the adverse event at grade 2 or grade 3 between Day X and Day Y
At least grade 3	All subjects with at least one occurrence of the adverse event at grade 3 between Day X and Day Y

10.1.2.4. Unsolicited adverse events

Unsolicited AE summaries are including SAEs unless specified otherwise.

Missing severity, relationship with study vaccine, and outcome of unsolicited adverse events will not be replaced and will appear as 'UNKNOWN' in all statistical output.

10.1.3. Data derivation

10.1.3.1. Temperature

Temperatures will be presented in degrees Celsius (°C). Temperatures reported in degrees Fahrenheit (°F) will be converted as follows:

$$\text{Temperature (Celsius)} = ((\text{Temperature (Fahrenheit)} - 32) \times 5)/9$$

10.1.3.2. Numerical serology results

Numerical serology results will be derived from the content of IS.ISORRES in the SDTM dataset. For assays with a specific cut-off, the following derivation rules apply:

IS.ISORRES	Derived value
"value" and value is < cut-off	cut-off/2
"value" and value is >= cut-off	value
All other cases	missing

10.1.3.3. Geometric mean concentrations (GMCs)

Geometric Mean Concentration (GMC) calculations are performed by taking the inverse logarithm of the mean of the log titre or concentration transformations. Antibody titres or concentrations below the cut-off of the assay will be given an arbitrary value of half the cut-off of the assay for the purpose of GMC calculation. The cut-off value is defined by the laboratory before the analysis and is described in the protocol.

10.1.3.4. Onset day

The onset day for an event (e.g. AE, medication, vaccination) is the number of days between the last study vaccination and the start date of the event. This is 1 for an event occurring on the same day as a vaccination (and reported as starting after vaccination).

10.1.3.5. Duration of events

The duration of an event with a start and end date will be the number of days between the start and end dates plus one day, i.e. an event that starts on 03MAR2018 and ends on 12MAR2018 has a duration of 10 days.

The duration of solicited events will be calculated as the sum of the individual days with the adverse event reported at grade 1 or higher during the solicited adverse event period.

10.1.3.6. Counting rules for combining solicited and unsolicited adverse events

For output combining solicited and unsolicited adverse events, all serious adverse events will be considered general events since the administration site flag is not included in the expedited adverse event CRF pages.

Multiple events with the same preferred term which start on the same day are counted as only one occurrence.

10.1.3.7. Counting rules for occurrences of solicited adverse events

When the occurrences of solicited AEs are summarized, each event recorded as having occurred during a specific period will be counted as only one occurrence regardless of the number of days on which it occurs. Also, in the case of co-administered study vaccines, an injection site reaction recorded for a subject following multiple vaccines will be counted as only one occurrence.

10.1.4. Display of decimals**10.1.4.1. Percentages**

Percentages and their corresponding confidence limits will be displayed with:

- no decimals when there are fewer than 50 subjects in each tabulated group
- one decimal when there are at least 50 subjects in at least one tabulated group
 - Exceptions will be made for percentages that are not 0% or 100% but appear as 0% or 100% due to rounding. For these specific cases the number of decimals will be increased until the displayed value is no longer 0% or 100%. Examples are given in the following table.

n/N	Displayed percentage
10/45	22%
1/45	2%
10/55	18.2%
1/55	1.8%
1/300	0.3%
1/3000	0.03%
1/30000	0.003%
299/300	99.7%
2999/3000	99.97%
29999/30000	99.997%

- The display of additional decimals for values close to 0% or 100% will be applied only to point estimates and not confidence limits, which can be rounded and displayed as 0% or 100%.
- Values of exactly 0% or 100% will be presented with no decimals regardless of the number of subjects per tabulated group.

10.1.4.2. Differences in percentages

Differences in percentages and their corresponding confidence limits will be displayed with one more decimal than the maximum number used to display the individual percentages, for example the difference between two percentages displayed with one decimal will be displayed with two decimals.

10.1.4.3. Serological summary statistics

The number of decimals used when displaying GMC and their confidence limits is shown in the following table:

GMC value	Number of decimals to display
<0.1	3
≥0.1 and <10	2
≥10 and <1000	1
≥1000	0

When multiple categories of GMC values are present in the same table, the number of decimals displayed should match that of the smallest category (i.e. the one with the higher number of decimals). For example, if GMC values of <0.1 appear in the same table as values of ≥0.1 and <10, 3 decimals should be displayed for both.

